6.3 Dose modifications

6.3.1 Dose modification and dose delay

For patients who do not tolerate the protocol-specified dosing schedule, dose adjustments are permitted in order to allow the patient to continue the study treatment, except during the first two cycles when dose modifications are only allowed if the patient experiences a DLT. The following guidelines need to be applied:

- If a patient experiences an AE meeting the criteria for DLT as outlined in Section 6.2.4, treatment should be withheld. Dose modifications for toxicities related to the study medication are summarized in Table 6-4. Following resolution of the toxicity to Grade 1 or to the patient's baseline value, the patient may resume study treatment at a lower dose level than is being tested at that time (on the same dosing schedule), if there is no evidence of disease progression as per irRC. A decision to resume treatment following the occurrence of a DLT is at the discretion of the Investigator. Following an AE meeting criteria for DLT, if a patient resumes study treatment, it should be at the next lower dose level. Dose reductions to doses below MCS110 0.3mg/kg / PDR001 100 mg Q3W are not permitted. If more than 2 consecutive doses have to be skipped due to study treatment-related toxicities, then the patient must be discontinued from the study unless the patient experiences clinical benefit in the opinion of the investigator. In this case, treatment can be continued at a dose agreed by Novartis and the investigator.
- For clinical management of suspected immune-related events, reference to consensus management guidelines is recommended such as those provided in the National Comprehensive Cancer Network (NCCN) Guidelines for the Management of Immunotherapy-Related Toxicities (available at : https://www.nccn.org/professionals/physician_gls/default.aspx#immunotherapy), the American Society for Clinical Oncology clinical practice guideline for Management of Immune-Related Adverse Events in Patients Treated With Immune Checkpoint Inhibitor Therapy (Brahmer 2018) or the European Society for Medical Oncology (ESMO) Clinical Practice Guidelines for Management of Toxicities from Immunotherapy (Haanen 2017). Note that in general, study treatment should be interrupted for grade 3 and 4 toxicities and for a subset of lower grade toxicities.

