- Consider early referral to specialists with expertise in the diagnosis and management of immune-related AEs to thoroughly investigate events of uncertain etiology.
- Events not included in the study protocol or the reference guidance documents should be managed per institutional preference.

- If one of the study drugs is discontinued the patient may continue with the remaining study drug, if the investigator considers it to be in the patient's best interest. The dose of the remaining study drug must be agreed by Novartis and the investigator.

Patients who discontinue the study treatment for a study related AE or a study-related abnormal laboratory value must be followed as described in [Section 6.3.2](#).

Table 6-4 Dose modification for drug related toxicities

Toxicity	Dose Adjustment Rules*
Hematology	
Neutropenia (ANC)	
Grade 3 or Grade 4.	Hold study treatment. Upon resolution to \leq Grade 2 or baseline within \leq 7 days, resume study treatment without dose modification, after discussion with the Novartis Medical Monitor
Febrile neutropenia	
Grade 3 or Grade 4	Hold study treatment. Upon resolution of fever and improvement of neutropenia to \leq Grade 2 or baseline, resume study treatment without dose modification, after discussion with the Novartis Medical Monitor.
Thrombocytopenia	
Grade 3	Hold study treatment. Upon resolution to \leq Grade 2 or baseline, resume study treatment without dose modification. For Grade 3 associated with major bleeding, discontinue study treatment.
Grade 4	Discontinue study treatment.
Anemia	
Grade 3 or Grade 4	Hold study treatment. Upon resolution to \leq Grade 2 or baseline within \leq 7 days, resume study treatment without dose modification.
Lymphopenia	
Any grade	Treatment-related lymphopenia does not require study treatment hold or discontinuation.
Gastrointestinal	
Diarrhea/colitis*	
Grade 1	May continue study treatment without dose modification. Manage per institutional standard guidelines which should include anti-diarrheal treatment, consideration of corticosteroid therapy, and hydration.
Grade 2	Hold study treatment. GI consultation. Upon resolution to \leq Grade 1 and tapering of steroid requirement to \leq 10 mg prednisone per day, resume study treatment without dose modification after discussion with the Novartis Medical Monitor.

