6.3.2 Follow-up for toxicities

Patients whose treatment is interrupted or permanently discontinued due to an AE or clinically significant laboratory value, must be followed-up at least once a week (or more if clinically indicated) for 4 weeks, and subsequently at approximately 4-week intervals, until resolution or stabilization of the event, whichever comes first. Appropriate clinical experts should be consulted as deemed necessary. Consensus management algorithms for immune-related AEs have been developed and are available to assist investigators in assessing and managing immune-related AEs (refer to [Section 6.3.1](#)). In case of a toxicity suspected to be a cytokine release syndrome, the assessments outlined in [Section 7.2.2.5.5](#) must be performed.

All patients must be followed up for AEs and SAEs for 150 days after the last dose of PDR001 or 90 days after the last dose of MCS110 for patients who stopped PDR001 and continued MCS110 alone for more than 60 days.

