- Patients with confirmed irPD will discontinue study drug(s) and enter the Follow-up period (see [Section 7.1.5](#)). Patients who have either a poor performance status or toxicity requiring both MCS110 and PDR001 discontinuation and do not have a confirmed irPD will enter the Follow-up period until confirmed irPD, initiation of a new treatment, completion of all Follow-up visits. Patients will then enter the Survival Follow-up period.
- Patients with confirmed PD/irPD in stable or improved clinical status can remain under treatment, after discussion with Novartis, until there is a further progression or clinical deterioration under the following circumstances:
 - Absence of signs and symptoms (including worsening of laboratory values) indicating disease progression;
 - No decline in ECOG performance status;
 - Absence of rapid progression of disease;
 - Absence of progressive tumor at critical anatomical sites (e.g., cord compression) requiring urgent alternative medical intervention.

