7.1.3 Discontinuation of Study Treatment

Patients may voluntarily discontinue from the study treatment for any reason at any time. If a patient decides to discontinue from the study treatment, the investigator must make every effort (e.g. telephone, e-mail, letter) to determine the primary reason for this decision and record this information in the patient's chart and on the appropriate CRF pages. They may be considered withdrawn if they state an intention to withdraw, fail to return for visits, or become lost to follow-up for any other reason.

The investigator should discontinue study treatment for a given patient if, on balance, he/she believes that continuation would be detrimental to the patient's well-being.

Study treatment may be discontinued if any of the following occur:

- Adverse event
- Lost to follow-up
- Physician's decision
- Progressive disease per irRC (not per RECIST v1.1)

- Study terminated by Novartis
- Subject/guardian decision
- Protocol deviation

Study treatment must be discontinued in case of pregnancy.

At the time patients discontinue study treatment, a visit should be scheduled as soon as possible, and within 14 days of the last dose of study treatment or within 14 days of the decision to permanently discontinue study treatment, at which time all of the assessments listed for the EOT visit will be performed (Table 7-1). If the decision to withdraw the patient occurs at a regularly scheduled visit, that visit may become the EOT visit rather than having the patient return for an additional visit. An End of Treatment Phase Disposition CRF page should be completed, giving the date and reason for stopping the study treatment. End of treatment/Premature withdrawal visit is not considered as the end of the study.

Patients who discontinue study treatment should NOT be considered withdrawn from the study. They should return for the assessments indicated in Section 7.1.5. If they fail to return for these assessments for unknown reasons, every effort (e.g. telephone, email, letter) should be made to contact them as specified in Section 7.1.6. If a patient discontinues study treatment, but continues study assessments, the patient remains on study until such time as he/she completes protocol criteria for ending study assessments. At that time, the reason for study completion should be recorded on the Study Phase Completion Disposition CRF page.

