2.5.3 Handling of missing values/censoring/discontinuations

Patients in the dose escalation part who are ineligible for the DDS will be excluded from the primary analysis, although their data will be used for all remaining analyses.

Patients in the phase II part who have BOR of unknown (UNK) or not assessed (NA) will be considered as a treatment failure in the primary analysis of ORR according to RECIST v1.1.

If any alternative cancer therapy is taken while on study any subsequent efficacy assessments would be excluded from all relevant efficacy summary.

Continuing events (e.g., AEs, concomitant medication, etc.) will be summarized using the data cut-off date as the date of completion, with a flag to indicate within listings that the event is continuing. For patients who discontinue the study with ongoing events, the discontinuation date will be used as the completion date of the event.

The reason for discontinuation from study will be summarized and listed.

Other missing data will simply be noted as missing on appropriate tables/listings.

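### Section 6.3.1 takes some patients who stop for toxicity off the study, while its own closing paragraph and Sections 6.3.2, 7.1.2, 7.1.3 and 7.1.5 keep them in follow-up; the passages must be reconciled

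*Protocol*

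**What the plan says.** The trigger in Protocol Section 6.3.1 is: "If more than 2 consecutive doses have to be skipped due to study treatment-related toxicities". The consequence is: "then the patient must be discontinued from the study unless the patient experiences clinical benefit in the opinion of the investigator". For patients judged to benefit, the section adds: "In this case, treatment can be continued at a dose agreed by Novartis and the investigator".

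Other text points the other way:

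- **Section 6.3.1, closing paragraph:** "Patients who discontinue the study treatment for a study related AE or a study-related abnormal laboratory value must be followed as described in" Section 6.3.2.
- **Section 6.3.2:** "All patients must be followed up for AEs and SAEs for 150 days after the last dose of PDR001", with a 90-day alternative for patients who went on with MCS110 alone for more than 60 days. Patients stopped for an adverse event are also seen weekly for 4 weeks and then about every 4 weeks until the event resolves or stabilizes.
- **Section 7.1.2:** patients with "toxicity requiring both MCS110 and PDR001 discontinuation and do not have a confirmed irPD will enter the Follow-up period", and afterwards survival follow-up.
- **Section 7.1.3:** "Patients who discontinue study treatment should NOT be considered withdrawn from the study". Adverse event is one of the listed reasons for stopping treatment.
- **Section 7.1.5:** safety follow-up covers all patients, toxicity is not among the reasons that exempt a patient from progression scans, and survival follow-up covers everyone enrolled.

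SAP Section 2.5.3, like Protocol Section 10.4.3, attaches a consequence to leaving the study: "For patients who discontinue the study with ongoing events, the discontinuation date will be used as the completion date of the event".

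**The concern.** The protocol keeps two states apart: off treatment and off study. Section 7.1.3 records them on separate disposition pages, and Table 6-4, in the same section as the skipped-dose rule, speaks of discontinuing treatment. The skipped-dose rule names the study instead, and does so with a mandatory verb.

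The word matters because leaving the study has effects elsewhere. Section 4.1 lets it end progression follow-up, and Section 4.3 counts it toward the 80% criterion for the end of the study. Appendix 1 (Section 14.1.4.3) lists adverse event as a reason for study phase completion, so a site would have a way to record such an exit.

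At stake is follow-up in patients with prolonged treatment-related toxicity and no perceived benefit. Exit would depend partly on how the patient was judged to be doing, so the resulting PFS or OS censoring could not be assumed unrelated to prognosis.

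**Working it through.** The plan states no figure to reproduce. The check is a comparison of passages, followed by short arithmetic for the literal reading.

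**1. Do the passages conflict?** Section 6.3.1 orders the patient off the study. Sections 6.3.2 and 7.1.5 require safety follow-up of all patients, and 7.1.5 requires survival follow-up of all enrolled patients, with no exemption for patients removed under 6.3.1. Sections 7.1.2 and 7.1.3 keep patients who stop for toxicity on study. The instructions are incompatible as worded.

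**2. When would a literal exit fall?**
- Cycle length is 21 days (Section 7.1.2).
- More than 2 consecutive skipped doses means at least 3.
- The third falls due 3 × 21 = 63 days after the last dose given.
- Section 6.1.1 allows a delay of up to 7 days before a dose counts as skipped, so the latest date is about 63 + 7 = 70 days.

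**3. How much safety follow-up would be lost?** The window is 150 days after the last PDR001 dose, assuming both drugs stopped together.
- Exit at day 63: 150 − 63 = 87 days lost; 87/150 = 58%.
- Exit at day 70: 150 − 70 = 80 days lost; 80/150 = 53%.

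**4. Which analyses would be touched?**

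| Analysis | Relevant rule | Effect of exit at day 63 to 70 |
|---|---|---|
| ORR | Best overall response excludes assessments more than 30 days after last dose (SAP 2.1.1) | None; closed earlier |
| On-treatment AE tables | Close 30 days after last dose (SAP 2.8) | None; closed earlier |
| AE summaries adding the post-treatment period | Related events, patients receiving PDR001 (SAP 2.8) | Exposed |
| PFS | Censored at last valid assessment (SAP 2.7.3) | Exposed |
| DOR | Responders only; censored as for time to progression (Appendix 1) | Exposed, but only for a responder judged not to be benefiting |
| OS | Censored at last date known alive (Appendix 1) | Exposed |

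The stable-disease part of CBR may also be exposed if scans after that date are used to establish its duration.

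**5. How many patients?** The documents do not say, so steps 2 and 3 give the loss per affected patient only.

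**The case against.** The strongest reply is that the protocol already requires the follow-up. The closing paragraph of 6.3.1 sends patients who stop for an adverse event to 6.3.2, and 7.1.2, 7.1.3 and 7.1.5 carry them through safety, progression and survival follow-up. The context suggests that treatment was meant: the rule sits in a bullet about withholding and resuming doses, and its exception speaks of continuing treatment. Section 7.2.1 also uses the word study loosely, writing of study discontinuation for progression where 7.1.3 lists progression as a reason to stop treatment. This stands. It turns the harm from a planned loss into a risk at a site that acts on 6.3.1 alone, but it does not remove the contrary mandatory sentence.

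A reader might infer more, and the documents do not support it:

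- **That the protocol itself cuts off follow-up.** Four other sections and the end of 6.3.1 say otherwise.
- **That the patients affected have the most toxicity.** Table 6-4 sends many of the severest events straight to treatment discontinuation, without any skipped-dose count. Prolonged treatment-related toxicity is as far as the text goes.
- **That a given share of a group's PFS or OS data is lost.** No count is stated, and a censored patient still contributes time up to censoring.
- **That unresolved toxicity would be recorded as resolved.** The closing-date convention in SAP 2.5.3 is general. Outcome is collected separately and includes a not-resolved category (Protocol 8.1.1), and SAP 5.1.2 imputes no adverse event end dates.

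The prospective effect is also small. The last patient was enrolled on 10-Jan-2019, and on 08-Jul-2019 only 6 patients were on treatment and 41 in survival follow-up. If the study ends by the transfer route added in Amendment 05, progression and survival follow-up stop for everyone.

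**Conclusion.** The conflict is real: one mandatory sentence in 6.3.1 cannot be obeyed together with 6.3.2, 7.1.2, 7.1.3 and 7.1.5. Its weight is minor to moderate. For a patient handled literally under 6.3.1, 80 to 87 of 150 safety days (53% to 58%) and any later progression and survival data would be lost. This assumes that exit occurs when the third consecutive dose is missed, that both drugs stopped together, and that progression and survival follow-up would otherwise still be running. Sample size, ORR and the on-treatment adverse event tables are unaffected. Whether any patient was handled this way, and so whether any estimate changed, cannot be determined from the documents.

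**What to change.** Reconcile Section 6.3.1 with Sections 6.3.2, 7.1.2, 7.1.3 and 7.1.5, so that the text states whether the skipped-dose rule ends study treatment or study participation, and add a cross-reference to the follow-up those sections already require. The threshold for skipped doses and the clinical-benefit exception are not questioned here and stay as they are.

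Before database lock, list every patient with 3 or more consecutive doses skipped for treatment-related toxicity and check whether any was recorded as leaving the study for that reason. For each one, confirm the adverse event end dates and the PFS, DOR and OS censoring dates, and report the number in the CSR, including if it is zero.

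The cost is a wording correction and one data listing. No visit is added beyond those the protocol already requires.

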Lastly, PK and IG assessments are no longer mandated at the End of Treatment visit as sufficient data have already been collected.

Study Status

The CMCS110Z2102 study started enrollment on 29-Jun-2016. The last patient was enrolled on 10-Jan-2019. The pre-defined decision criteria for further expansion of the pancreatic cancer, TNBC, endometrial cancer and melanoma groups were not met (see Section 4.2 and 10.4.4.2). By consequence, no further patients will be enrolled in this study. A total of 141 patients have been treated: 60 patients in the dose escalation part and 81 patients in Phase II part of study (20 in pancreatic group, 20 in TNBC group, 21 in endometrial group and 20 in melanoma group). As of 08-Jul-2019, 6 patients were still on treatment (in phase II only) and 41 patients in survival follow-up.

Changes to the protocol

Changes to specific sections of the protocol are shown in the track changes version of the protocol using strike through red font for deletions and red underline for insertions.

Section 4.3: Definition of end of study:

- Addition of language to account for patients who would transfer into another study or an alternative treatment option to continue provision of study treatment.

Section 5.3: Exclusion criteria:

- Re-insertion of exclusion criteria 21 for Korea only where the use of condom for male study participants remains mandatory.

Section 7.1.3: Discontinuation of study treatment:

- Addition of language to specify that patients who transfer to another study or an alternative treatment option to continue provision of study treatment will complete end of treatment procedures.

Section 7.1.5: Follow up period:

- Addition of language to specify that patients who transfer into another study or an alternative treatment option to continue provision of study treatment will not complete the

safety, disease progression and survival follow up. For all other patients, the safety evaluation period will be completed but the disease-progression and survival follow up will not be performed or pursued.

Section 7.2.3: Pharmacokinetics and immunogenicity assessments, Table 7-1: Visit evaluation schedule and Table 7-7: Phase II Part: Pharmacokinetic blood collection log for MCS110, PDR001 and IG samples:

- Removal of PK and IG samples collection at End of Treatment.

Section 8.3: Pregnancies:

- Re-insertion of the pregnancy outcome collection for the female partners of any males which remains valid for Korea only.

IRBs/IECs

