Fatigue lasting < 7 days.
Immune-related adverse events persisting at Grade3 < 7 days after treatment with corticosteroids.
*CK elevation without associated muscle damage per investigator discretion
*Isolated AST elevations (without bilirubin or ALT elevations \geq Grade 1)
The following Grade 2 AEs will be considered as DLTs:
Total bilirubin $> 2 \times$ ULN with \geq CTCAE Grade 2 AST/ALT.

Pneumonitis persisting > 7 days despite treatment with corticosteroids.
Eye pain or reduction of visual acuity that does not respond to topical therapy and does not improve to Grade 1 severity within 2 weeks of the initiation of topical therapy OR requires systemic treatment.
Other clinically significant toxicities, including a single event or multiple occurrences of the same event may be considered as DLT's.
* MCS110 treatment results in CK and AST elevations without any association to muscle damage (Radi 2011). The CK/AST elevations are caused by reduced clearance rate from the circulation due to the diminished numbers of macrophages (Kupffer cells) in the liver (Section 1.2.2.1).

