Grade 3	Hold study treatment. GI consultation. Upon resolution to \leq Grade 1 and tapering of steroid requirement to \leq 10 mg prednisone per day, consider resuming study treatment after discussion with the Novartis Medical Monitor.
Grade 4	Discontinue study treatment.

Toxicity	Dose Adjustment Rules*
Hepatic (AST and/or ALT elevation)	
Grade 2 AST and/or ALT	Hold study treatment. Manage per institutional practice. Upon resolution to \leq Grade 1 or baseline, consider resuming study treatment without dose modification.
Grade 2 transaminitis with bilirubin $>1.5 \times$ ULN (unless Gilbert's syndrome)	Discontinue study treatment.
Grade 3 AST and/or ALT	Hold study treatment. Manage per institutional practices. Upon resolution to \leq Grade 1 or baseline within 7 days, consider resuming study treatment without dose modification after discussion with the Novartis Medical Monitor. Otherwise, discontinue study treatment
Grade 4 AST and/or ALT	Discontinue study treatment.
Isolated total bilirubin elevation**	
Grade 2	Hold study treatment. Upon resolution to \leq Grade 1 or baseline, may continue study treatment without dose modification.
Grade 3	Hold study treatment. Upon resolution to \leq Grade 1 or baseline, may consider resuming study treatment after discussion with the Novartis Medical Monitor.
Grade 4	See footnote**. Otherwise, discontinue study treatment.
Asymptomatic amylase and/or lipase elevation***	
Grade 3 or Grade 4, not associated with symptoms or clinical manifestations of pancreatitis***	Continue study treatment. If levels do not resolve to \leq Grade 2 within \leq 14 days after the initial report, hold study treatment. Upon resolution to \leq Grade 2, may resume study treatment without dose modification, after discussion with the Novartis Medical Monitor.
Pancreatitis	
Grade 2 / radiologic evidence	Hold study treatment. Manage per institutional practice. Upon resolution to \leq Grade 1, may resume study treatment without dose modification, if no clinical evidence of pancreatitis and after discussion with the Novartis Medical Monitor.
Grade 3-4	Discontinue from treatment.
CK elevation	

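### Table 6-4 stops treatment for Grade 2 AST/ALT with bilirubin above 1.5 x ULN but allows resumption to be considered when the AST/ALT rise is Grade 3

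*Protocol*

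**What the plan says.** Protocol Section 6.3.1, Table 6-4, treats AST/ALT elevation in four rows:

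- Grade 2 AST and/or ALT: hold; resumption may be considered once values are back to Grade 1 or lower, or to baseline.
- "Grade 2 transaminitis with bilirubin" above 1.5 x ULN, unless Gilbert's syndrome: discontinue.
- Grade 3 AST and/or ALT, with no mention of bilirubin: hold; on return to Grade 1 or lower, or to baseline, the row continues "within 7 days, consider resuming study treatment without dose modification after discussion with the Novartis Medical Monitor. Otherwise, discontinue study treatment".
- At Grade 4 for either enzyme, treatment stops.

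The bilirubin rows that follow are headed as isolated elevations. Their footnote concerns purely indirect hyperbilirubinemia.

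Table 6-3 (Section 6.2.4) handles the same combination differently. It counts total bilirubin above 2 x ULN as dose-limiting when it occurs with "CTCAE Grade 2 AST/ALT", and the sign just before those words is greater-than-or-equal, so Grade 3 is included. Its Grade 3 exception for AST is restricted to "Isolated AST elevations (without bilirubin or ALT elevations" of Grade 1 or higher).

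**The concern.** A dose-modification table should not become more permissive as the event worsens. Section 1.3.4 expects overlapping liver enzyme elevations with this combination. It attributes the CK and transaminase rises under MCS110 to reduced clearance by liver macrophages, and it suspects a class effect of immune-related hepatitis for PDR001. A bilirubin rise alongside the enzymes helps separate a pharmacological enzyme rise from liver injury. The Grade 2 combined row uses that information; the Grade 3 row does not.

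At stake is a patient-safety rule. For Grade 3 AST/ALT with raised bilirubin that recovers quickly, the written rule leaves to discussion what it forbids outright for the milder event.

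**Working it through.** This is a comparison of wording; the plan states no figure to reproduce.

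**Step 1. Apply the rows to one situation.** Take bilirubin above 1.5 x ULN in a patient without Gilbert's syndrome.

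| AST/ALT grade | Row that applies | Action |
|---|---|---|
| 2 | Combined Grade 2 row | Discontinue |
| 3 | Grade 3 row (bilirubin not mentioned) | Hold; resumption may be considered if recovered within 7 days, otherwise discontinue |
| 4 | Grade 4 row | Discontinue |

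Discontinuation is mandatory at 2 of the 3 grades, and the exception is the middle one.

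**Step 2. Look for another rule that closes the gap.**

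- The isolated-bilirubin rows do not apply while AST/ALT are also raised.
- The bilirubin footnote is limited to Grade 3 or 4 elevation that is indirect only.
- The general DLT rule in Section 6.3.1 requires treatment to be withheld for an event meeting DLT criteria. It leaves resumption to the investigator, at the next lower dose level, so it still permits resumption. For such an event it also conflicts with the Grade 3 row, which resumes without dose modification.
- Section 6.3.1 says of suspected immune-related events that "reference to consensus management guidelines is recommended". That is a recommendation, and the content of those guidelines is not in the documents, so it is not relied on here.

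None of these requires discontinuation for the Grade 3 combined event.

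**Step 3. Check whether a patient must pass through the Grade 2 row.** If AST/ALT fall through Grade 2 while bilirubin is still above 1.5 x ULN, the combined row applies and treatment stops. This need not be observed. Section 6.3.2 sets minimum follow-up after interruption at once a week, and the Grade 3 row allows 7 days for recovery, so a patient can be Grade 3 at one check and Grade 1 or lower at the next. The gap is also open if bilirubin normalises first, or if the Grade 2 row is read as not covering an event that peaked at Grade 3.

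**Step 4. Prospective reach.** The Study Status text under Amendment 05 reports 141 patients treated, 81 of them in Phase II. It also says that "The last patient was enrolled on 10-Jan-2019" and that, as of 08-Jul-2019, "6 patients were still on treatment (in phase II only").

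- Share of all treated patients still on treatment: 6/141 = 4.3%.
- Share of Phase II patients still on treatment: 6/81 = 7.4%.
- Days from last enrolment to that count: 21 (rest of January) + 28 + 31 + 30 + 31 + 30 + 8 = 179.

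These are shares still exposed to the rule, not shares affected. The documents give no rate for Grade 3 AST/ALT with raised bilirubin.

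**The case against.** The strongest objection is that Table 6-4 does not stand alone. Under Table 6-3, Grade 3 ALT generally meets DLT criteria, and Grade 3 AST loses its exception once bilirubin is raised. Section 6.3.1 then calls for withholding treatment and, if it resumes, the next lower dose level. That makes the Grade 3 outcome stricter than the row alone suggests. It stands as a qualification but does not remove the inversion, because resumption stays possible at Grade 3 and is barred at Grade 2. Table 6-3 also has a carve-out for immune-related events that stay at Grade 3 for less than 7 days after corticosteroids, and the formal DLT window is the first two cycles of Phase Ib.

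Table 6-3 is also an imperfect comparator. It classifies DLTs, uses 2 x ULN rather than 1.5 x ULN, and does not order discontinuation. That is fair: it shows that the open-ended grade was available to the drafter, but it sets no discontinuation standard.

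A sensible clinician would treat the Grade 2 combined rule as a floor, the Medical Monitor would probably catch the case, and Section 7.1.3 tells the investigator to stop treatment judged detrimental. All of this reduces the practical risk. It relies on judgement where the milder event has a flat rule.

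Finally, few patients remain and no event rate is known. That is correct, and it is why the point is rated minor.

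**Conclusion.** The concern holds as a minor design point, with high confidence. As written, Table 6-4 requires discontinuation for Grade 2 and Grade 4 AST/ALT with bilirubin above 1.5 x ULN outside Gilbert's syndrome, but not for Grade 3, and nothing else in the protocol supplies the missing rule. No rationale is given for the difference.

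The size is small. At most 6 patients could meet the rule after 08-Jul-2019, assuming no enrolment after the stated closure. How many earlier patients were treated under this wording cannot be determined from the documents. No endpoint, analysis or sample size changes.

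**What to change.** Change two row labels in Table 6-4:

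- Combined row: Grade 2 or higher AST and/or ALT with bilirubin above 1.5 x ULN (unless Gilbert's syndrome); action unchanged, discontinue.
- Grade 3 row: Grade 3 AST and/or ALT with bilirubin at or below 1.5 x ULN, or with Gilbert's syndrome; action unchanged.

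The table already splits a Grade 3 row by an aggravating feature. Grade 3 thrombocytopenia can resume after recovery, but "For Grade 3 associated with major bleeding, discontinue study treatment".

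The cost is an amendment or an investigator letter. No new assessment is needed, because total bilirubin is already in the chemistry panel (Table 7-4). The downside is possibly a few more discontinuations among the 6 patients still on treatment, including some who would have recovered within 7 days.
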